10.4.4 Safety Analyses

Safety analyses will be performed on the Safety analysis set. Safety data, including frequency of events and proportion of participants experiencing events described in section 8.1, clinical laboratory tests, vital signs, and physical examinations, will be summarized descriptively overall and by treatment group. For categorical safety outcomes, numbers and percentages will be used. For continuous safety outcomes, number, mean, standard deviation, median, interquartile range, minimum and maximum will be used to summarize changes from baseline to each study visit in laboratory tests and vital signs. Percent change from baseline will be added for laboratory values as outlined in the SAP. The primary organ system associated with each adverse event will be coded by the medical monitor. Kaplan-Meier methods will be used to summarize graphically the time to treatment failure, treatment emergent AEs and SAEs that result in discontinuation of treatment, and death.

10.4.5 Adherence & Retention Analyses

Participant disposition will be summarized descriptively. The number and percentage of participants randomized, completed, and withdrawing, along with reasons for withdrawal, will be tabulated overall, and by treatment group. The number of participants in each analysis population will be reported. Other disposition and study conduct information, including major protocol violations will be summarized. Duration of the study follow-up will be summarized overall and by treatment group.

Compliance with study medication will be assessed and summarized, including the proportion of participants who adhered to study treatment at each study visit, the median duration of adherence to study treatment and the proportion of participants who permanently discontinued study medication by reason for treatment permanent discontinuation, overall and by treatment group.

10.4.6 Baseline Descriptive Statistics

Prior to analysis, the two treatment groups will be compared descriptively with respect to demographic and baseline variables (e.g., age, race, FVC-%, mRSS). No statistical tests will be used to compare the treatment groups.

10.4.7 Planned Interim Analyses

10.4.7.1 Safety Review

Safety outcomes will be presented at each DSMB meeting. These include number of and proportion of subjects with SAEs (including segregation of those involving deaths), treatment-emergent AEs, AEs of Special Interest, discontinuation of study medication due to AEs, and

protocol-defined treatment failures. These presentations will be descriptive, with no formal inferential methods used. Given that these study medications have been approved for other indications, their safety profile has been well characterized. Thus, no specific rules for halting study enrollment or study interventions for safety are specified; however, the DSMB may request formal inferential testing to assess the risk-benefit profile of these study medications in this study population.

10.4.7.2 Efficacy Review

No interim analysis is planned.

10.4.8 Additional Sub-Group Analyses

No other sub-group analyses (other than those described above for the primary and secondary efficacy endpoints) are planned.

10.4.9 Multiple Comparison/Multiplicity Analyses

No adjustments for multiplicity are planned since there is one primary analysis of the primary endpoint at the end of the study. Secondary analyses of the primary endpoint and analyses of the secondary endpoints serve to assess the robustness of the results and consistency of treatment effect on clinical outcomes important in this disease.

10.4.10 Tabulation of Individual Response Data

SAEs, deaths, and AEs resulting in discontinuation of study medication will be tabulated for participants who experience these events.

10.4.11 Exploratory Analyses

Additional analyses may be performed to explore both safety and efficacy measures collected in this study. The precise methods and analyses will be determined after the database is locked and the blind is broken. Thus all such analyses will be interpreted cautiously and not used for formal inference, although inferential statistics may be used as part of the data summary.

10.5 SAMPLE SIZE

10.5.1 Introduction & Background to Sample Size Determination

An initial sample size target of 150 participants (up to 190 consented and screened subjects to achieve 75 randomized per treatment group) was identified based on recent clinical trial experience and logistical considerations including the number of clinical centers with appropriate leadership and infrastructure to be considered as state of the art for treating SSc-ILD. Statistical analysis, using a clinical trials simulation approach, was then employed to estimate the power to detect various treatment effects on the primary endpoint with a two-sided Type I error of 5% and an 18-month attrition estimate of 24%.

Data from the SLS I and II clinical trials (44,50-52) were used to estimate the baseline characteristics of the proposed study population and their response over time to treatment with MMF, including the impact of prior treatment with MMF (occurring prior to study randomization), on the predicted

course of lung function changes over time. Note that SLS III will employ essentially the same patient recruiting centers and investigators as those that participated in the prior studies (with some new additions) and that the enrollment criteria have been relatively conserved over time to assure reproducibility. Furthermore, both the control arm and experimental arm of the proposed study will be treated with a course of cytotoxic therapy that is essentially identical to that reported from the SLS I and II studies. For the impact of PFD, safety and tolerability data from the LOTUSS trial (20) and outcome data from studies in which PFD was used to treat IPF (12-13) were considered informative.

10.5.2 Assumptions

Based on these available data, the following assumptions were used to generate clinical outcome scenarios for the potential response of FVC-% over time for both the control arm (MMF+Plac) and the experimental arm (MMF+PFD) of SLS III:

- 1) Data from SLS I and II were used as the best available data to estimate the standard deviation of the FVC-% values at different times in the study and the mean change in FVC-% at 3, 6, 9, 12, 15 and 18 months were assumed to follow a multivariate normal distribution, with equivalent variances in the two treatment groups.
- 2) In the same manner, data from the II study was used to inform the estimated impact of prior therapy with MMF, occurring prior to randomization, on the expected mean change in FVC-% and the variance of the FVC-% values at different times after randomization.
- 3) We measured the correlation structure over time for repeated measurement of the FVC-% in individual subjects participating in the SLS I study and applied that to the prediction of outcomes for SLS III. As one might assume, correlation between measurements taken at closer intervals is greater than measurements taken farther apart and from SLS I data the correlations among outcomes 3 months apart was 0.866, 6 months apart was 0.834, and 9 months apart was 0.802.
- 4) Treatment with cytotoxic therapy (MMF or CYC) is associated with an initial period of deteriorating lung function during the first 3-6 months of treatment that appears due to the required titration of cytotoxic medication over several months and the relatively slow clearing of existing immune mediators that drive inflammation and tissue destruction. This initial loss of lung function can average from -0.25% to -2.5%.
- 5) After an initial 3-6 month period that is associated with a relative decline of lung function, continued treatment with cytotoxic therapy is associated with a relative improvement in lung function over time that ranges from approximately +2.0 to +3.0% at 12 months and from approximately +3.0 to +5.0% at 18 months.
- 6) These time-dependent treatment response features, with an initial decline and delayed improvement, have a direct impact on the predicted course of the FVC-% over time in subjects who present to the study after several months of prior MMF therapy. The percentage of patients on cytotoxic therapy prior to randomization, and the length of prior treatment, need to be accounted for in predicting the overall course and magnitude of the change in FVC-% over time.
- 7) In contrast to the delayed effects of MMF, use of PFD for the treatment of IPF is associated with a rapid onset that slows the decline in lung function and is seen as early as 3 months.

8) In addition, given that the mechanisms of action for MMF and PFD are fundamentally different, it is reasonable to speculate that combination therapy (MMF+PFD) will have an overall impact on lung function at 18 months that is superior to either agent alone.

10.5.3 Defining the Primary Study Outcome

[figure not shown]
The primary aim of the study is to compare the impact of combining PFD and MMF in the experimental arm with that of MMF plus Plac in the control arm on pulmonary function during the 18-month double-blind period. The primary endpoint is change from baseline in the mean forced vital capacity, measured as the percentage of the age-, height-, gender- and race-adjusted predicted value (FVC-%) over the course of the 18-month double-blind treatment period. FVC is measured at baseline (pre-treatment) and then quarterly after treatment begins during the treatment period (i.e., months 3, 6, 9, 12, 15 and 18). Participants are required to have FVC-% \leq 85% at screening.

10.5.4 Clinical Trial Scenarios and Simulations to Estimate Study Power in Treatment Naïve Patients

Two outcome scenarios were considered based on the two potential mechanisms of action by which the addition of PFD might improve the response to treatment with MMF alone. Both scenarios assume that the average response pattern to MMF alone (the control arm) would approximate the average response pattern to cytotoxic therapy observed from SLS II. In that study, the overall improvement from baseline in the FVC-% was approximately 3.0% at the 12 month time point and 4.25% at 18 months. Two different response scenarios were then proposed to represent the range of possible responses in patients treated with combined MMF+PFD (the experimental arm).

- **In Scenario 1**, it is assumed that treatment with PFD is associated with an early slowing of the decline in lung function normally observed during the first 3-6 months of cytotoxic therapy and that there is only a small additive effect of PFD to the later improvement in lung function. The collective result is a 2.5% greater response to treatment at 12 months in the experimental versus control arms and this difference between the groups remains the same for the duration of the 18-month study.
- **In Scenario 2**, it is assumed that treatment with PFD is associated with both an early slowing of the decline in lung function and a definite additive effect on the overall improvement in FVC-% that continues throughout the entire treatment period. The collective result is a 3.125% greater response to treatment at 12 months in the experimental versus control arms which continues to slowly increase to a final 3.25% difference between the two groups at 18 months.

Figure 10.5.4. Hypothesized Response Trajectories over the 18-Month Double-Blind Treatment Period by Treatment Group with two scenarios considered, all participants naïve to therapy.

The power to detect a response based on each Scenario was then calculated by carrying out 1,000 clinical trials simulations for each scenario in SAS 9.4, using a linear mixed model with participant-month in the study (3, 6, 9, 12, 15 and 18) as the unit of analysis and the change from baseline in FVC-% as the outcome, with terms for treatment group, baseline FVC-%, month and the interaction of treatment group with month as a fixed covariate and participant as a random effect to account for the correlation of outcomes over time within a participant. (This is a simplification of the model used for the primary analysis of the primary endpoint described above.) We used a compound symmetry variance-covariance structure. The average power is calculated as the number of simulations where the F-test used to test the hypothesis that the mean change from baseline during the double-blind treatment period differs between the two treatment groups is rejected ($p \leq 0.05$) divided by the number of simulations. 95% CIs for power are calculated based on the exact binomial proportion.

Table 10.5.4. Power to detect differences in the response pattern from baseline to 18 months for the primary outcome (change in FVC-%) when comparing the course of change in lung function over time for the MMF+PFD arm and the MMF+Plac arm according to the two proposed outcome scenarios. Results assume a 5% two-sided type I error and are provided for three different sample sizes (N = 75/arm; 70/arm and 65/arm)

Assumptions:

- Drop-out rates, variances and data inter-correlations presented below are derived from SLS I and II data and assumed to be identical for the two defined scenarios
- A 5% two-sided type I error is assumed
- The difference in the outcome measure between treatment arms (relative difference in the change from baseline in absolute FVC %predicted) for each scenario was estimated based on the hypothetical response to PFD proposed for each scenario as detailed in **Figure 10.5.4**.

Scenario 1 Difference between treatment arms (FVC-%)	Scenario 2 Difference between treatment arms (FVC-%)	Dropout (Cumulative %)	SD Estimate	Assumed Correlations (AR1):
Mo 3: 0.5	Mo 3: 0.75	Mo 3: 6.5%	Mo 3: 4.1	3-mo intervals: 0.866
Mo 6: 1.375	Mo 6: 1.75	Mo 6: 13%	Mo 6: 5.1	6-mo intervals: 0.834
Mo 9: 2.25	Mo 9: 3.0	Mo 9: 17%	Mo 9: 6.2	9-mo intervals: 0.802
Mo 12: 2.5	Mo 12: 3.125	Mo 12: 20%	Mo 12: 6.9	12-mo intervals: 0.790

Mo 15: 2.5	Mo 15: 3.25	Mo 15: 23%	Mo 15: 6.2	15-mo intervals: 0.780
Mo 18: 2.5	Mo 18: 3.25	Mo 18: 24%	Mo 18: 6.2	

Power Calculations Scenario 1:

Evaluation of Statistical Power by sample size, adjusting for drop outs over time, based on 1000 clinical trial outcome simulations:

N per arm at baseline	N per arm at 18 mo	Estimated Statistical Power	95% Lower Bound of Statistical Power	95% Upper Bound of Statistical Power
75	57	82.3%	79.8%	84.6%
70	53	78.6%	75.9%	81.1%
65	49	76.3%	73.5%	78.9%

Power Calculations Scenario 2:

Evaluation of Statistical Power by sample size, adjusting for drop outs over time, based on 1000 clinical trial outcome simulations:

N per arm at baseline	N per arm at 18 mo	Estimated Statistical Power	95% Lower Bound of Statistical Power	95% Upper Bound of Statistical Power
75	57	95.6%	94.1%	96.8%
70	53	92.6%	90.8%	94.2%
65	49	91.8%	89.9%	93.4%

Note that with the given m-ITT design, the linear mixed effects model will actually include data from all subjects who have at least a baseline and one follow-up measure of FVC-. In this setting, even with an overall 24% attrition by the end of 18 months, it is estimated that 83% of the maximal possible study outcome data points (assuming no attrition) would be included in the analysis.

According to Scenario 1, which is strictly based on the documented capacity for PFD to slow the rate of decline of lung function in patients with IPF who are not receiving any other treatment, a sample size of 75 patients per treatment arm is required to obtain a minimum power of 80% (i.e., 80% is within the 95% CI for this prediction). If PFD has novel effects when combined with MMF so that it both reduces the rate of lung decline and works in concert with MMF to improve overall lung function (i.e., Scenario 2), then the predicted outcome will be much more reliably detected and a smaller sample size would be sufficient.

10.5.5 Impact of a Mixed Population of Treatment Naïve and Previously-treated Patients on the Estimate of Study Power

[figure not shown]
Having established adequate estimates of study power in a population of treatment naïve patients, the clinical trial Scenarios were then adjusted to assess the impact of a mixed starting population of patients in which some of the participants are treatment naïve and others have been on prior treatment with MMF (or DMARD with similar activity) for a period of 3, 6 or 9 months. Additional assumptions associated with these modified Scenarios include:

- 1) The mean change in FVC-% over a given 3-month interval and the corresponding impact on the standard deviation of the FVC-% measurement will always reflect the total time that a patient has been on therapy, including therapy that was administered before randomization and therapy that was administered following randomization.

2) The treatment effect is measured as the change from baseline, in which baseline is determined at the time of randomization (baseline visit). The baseline FVC-% measurement therefore establishes the zero reference value for evaluating change over time in response to the time that a patient is on the protocol. In this setting, patients who have been on 3 months or more of MMF will not be expected to experience the initial decline in lung function that occurs when enrolling treatment naïve patients.

3) As one of the hypothesized benefits of starting PFD and MMF at the same time in treatment naïve patients is the prevention of an early decline in lung function, there is a relative treatment penalty in the predicted PFD+MMF arm when patients have been on prior therapy with MMF. This results in less and less separation between the course of the two treatment arms as the length of time on prior MMF increases. This impact must be accounted for when modeling treatment outcomes and predicting study power.

Figure 10.5.5. Hypothesized Response Trajectories over the 18-Month Double-Blind Treatment Period by Treatment Group for Scenario 2 based on length of time on MMF therapy prior to randomization.

The power to detect a response according to Scenario 2, when taking into account the length of prior treatment with MMF (naïve, 3 mo, 6 mo and 9 mo strata) and the percentage of subjects within each of these strata, was then calculated by carrying out 1,000 clinical trials simulations for each situation in SAS 9.4 as already described. We varied the proportion of patients from 100% naïve down to 50% naïve, with the distribution across the prior treatment with MMF strata varied as described below. Estimates of the differences between treatment arms and the standard deviation

for the measurements at a given time were adjusted according to the scenario curves shown in Figure 10.5.5.

Table 10.5.5. Power to detect differences in the response pattern from baseline to 18 months for the primary outcome (change in FVC-%) when comparing the course of change in lung function over time for the MMF+PFD arm and the MMF+Plac arm according to Scenario 2 with different mixtures of treatment naïve patients and those who were on prior MMF therapy for 3, 6 or 9 months as indicated. Results assume a 5% two-sided type I error and are provided for three different sample sizes (N = 75/arm; 70/arm and 65/arm)

a. Scenario 2: N = 75 per arm

% per stratum (length of prior MMF)				Estimated statistical power based on 1000 clinical trial outcome simulations		
Naive	3 mo	6 mo	9 mo	Power	95% Lower Bound	95% Upper Bound
1.00	0.00			95.6%	94.1%	96.8%
0.80	0.20			93.8%	92.1%	95.2%
0.75	0.25			92.2%	90.4%	93.8%
0.70	0.30			90.8%	88.8%	92.5%
0.60	0.40			90.5%	88.5%	92.2%
0.50	0.50			86.1%	83.8%	88.2%
0.80	0.10	0.10		91.4%	89.5%	93.1%
0.70	0.20	0.10		89.5%	87.4%	91.3%
0.70	0.10	0.20		90.2%	88.2%	92.0%
0.60	0.30	0.10		89.0%	86.9%	90.9%
0.60	0.20	0.20		88.2%	86.0%	90.1%
0.60	0.10	0.30		85.2%	82.8%	87.3%
0.50	0.40	0.10		84.7%	82.3%	86.9%
0.50	0.30	0.20		82.7%	80.2%	85.0%
0.50	0.20	0.30		82.7%	80.2%	85.0%
0.50	0.10	0.40		79.7%	77.1%	82.2%
0.70	0.10	0.10	0.10	86.4%	84.1%	88.5%
0.60	0.20	0.10	0.10	86.2%	83.9%	88.3%
0.60	0.10	0.20	0.10	83.7%	81.3%	85.9%
0.50	0.30	0.10	0.10	79.9%	77.3%	82.3%
0.50	0.20	0.20	0.10	79.3%	76.7%	81.8%

b. Scenario 2: N = 70 per arm

% per stratum (length of prior MMF)				Estimated statistical power based on 1000 clinical trial outcome simulations		
Naive	3 mo	6 mo	9 mo	Power	95% Lower Bound	95% Upper Bound
1.00	0.00			91.8%	89.9%	93.4%
0.80	0.20			91.3%	89.4%	93.0%
0.70	0.30			88.1%	85.9%	90.0%
0.60	0.40			86.0%	83.7%	88.1%
0.50	0.50			84.6%	82.2%	86.8%
0.80	0.10	0.10		89.4%	87.3%	91.2%
0.70	0.20	0.10		88.7%	86.6%	90.6%
0.70	0.10	0.20		85.6%	83.3%	87.7%
0.60	0.30	0.10		85.7%	83.4%	87.8%
0.60	0.20	0.20		82.9%	80.4%	85.2%
0.60	0.10	0.30		81.5%	79.0%	83.9%
0.50	0.40	0.10		83.0%	80.5%	85.3%
0.50	0.30	0.20		81.5%	79.0%	83.9%
0.50	0.20	0.30		79.9%	77.3%	82.3%
0.50	0.10	0.40		79.9%	77.3%	82.3%

c. Scenario 2: N = 65 per arm

% per stratum (length of prior MMF)				Estimated statistical power based on 1000 clinical trial outcome simulations		
Naive	3 mo	6 mo	9 mo	Power	95% Lower Bound	95% Upper Bound
1.00	0.00			91.8%	89.9%	93.4%
0.80	0.20			88.2%	86.0%	90.1%
0.70	0.30			85.5%	83.2%	87.6%
0.60	0.40			81.4%	78.9%	83.8%
0.50	0.50			79.7%	77.1%	82.2%
0.80	0.10	0.10		87.1%	84.9%	89.1%
0.70	0.20	0.10		85.5%	83.2%	87.6%
0.70	0.10	0.20		83.2%	80.7%	85.5%
0.60	0.30	0.10		78.4%	75.7%	80.9%
0.60	0.20	0.20		77.5%	74.8%	80.0%

According to these predictions for Clinical Trial Scenario 2, representing the primary outcome to be investigated, the study is adequately powered (80% power or greater) to detect a difference between the two treatment arms when the sample size is 150 and the patient population contains at least 50% treatment naïve patients. If the remaining 50% of enrolled patients are limited to no more

than 6 months of prior therapy with MMF, then adequate power is maintained across the entire range of anticipated distributions between subjects with up to 3 mo of prior therapy and those with between 3 to 6 mo of prior therapy.

As a result, the target study population will consist of at least 50% of patients who are treatment naïve and up to 50% of patients who recently started on therapy within 6 months of entering the study (as detailed in Table 10.5.5 above). With this mixture of patients, the power remains adequate even if only 70 patients are enrolled in each arm (total randomization 140 patients), providing optimal flexibility for the enrollment phase of the study.

When a similar statistical approach is applied to Clinical Trial Scenario 1, in which only a small additive effect of PFD is modeled in addition to the underlying treatment response to MMF, the power to detect a difference between the two treatment arms is adequate (80% power or greater) when the sample size is 150 and the patient population contains at least 75% treatment naïve patients. When the percentage of treatment naïve patients is reduced to 50%, the predicted power is at best 75% (assumes % per stratum of 50% naïve, 40% 3 mo, 10% 6 mo).

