10.2 STATISTICAL HYPOTHESES

The primary hypothesis is that the rapid onset and anti-fibrotic effects of PFD, which have been observed in the treatment of Idiopathic Pulmonary Fibrosis (IPF), will complement the delayed anti-inflammatory and immunosuppressive effects of MMF, to produce a significantly more rapid and/or greater improvement in lung function over time than occurs in patients receiving control therapy with MMF (and Plac) alone. Statistically, the following null and alternative hypotheses will test the superiority of the combination of PFD+MMF versus MMF+Plac in improving the change from baseline in mean forced vital capacity (as a percentage of the age-, height-, gender- and race-adjusted predicted value, indicated as FEV-%) over the course of the 18-month double-blind treatment period (primary endpoint):

$$H_0: \Delta_{PFD+MMF} = \Delta_{MMF+Plac}$$

$$H_A: \Delta_{PFD+MMF} \neq \Delta_{MMF+Plac}$$

where Δ reflects the adjusted mean change from baseline trajectory over the 18-month treatment period.

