10.4.2 Analysis of the Primary Efficacy Endpoint

The primary endpoint is change from baseline in the mean forced vital capacity, measured as the percentage of the age-, height-, gender- and race-adjusted predicted value (FVC-%) over the course of the 18-month treatment period, as reported quarterly (i.e., months 3, 6, 9, 12, 15 and 18). Given that the trajectories of the primary endpoint are expected to differ because of the mechanisms of action of the two treatment modalities, a longitudinal approach incorporating all time points will be employed. Specifically, the endpoint will be analyzed using a linear mixed model with participant-month in the study (3, 6, 9, 12, 15, 18) as the unit of analysis and the change from baseline in FVC-% as the outcome, with terms for baseline FVC-%, treatment group, month, the interaction of month (x) treatment group, and prior MMF therapy (stratification factor: naïve, >0 to \leq 3 months, and >3 months to 6 months), as fixed covariates. Study participant will be treated as a random effect to account for the correlation of outcomes over time within a participant. The model generates adjusted estimates of change from baseline in the FVC-% for each treatment group and month, and an F-test will be used to test the hypothesis that the mean change from baseline during the treatment period differs between the two treatment groups. The model-based adjusted mean change from baseline in FVC-% will be presented graphically by treatment group by study month, with 95% confidence intervals (CIs) provided at each month.

The primary analysis of the primary efficacy endpoint will use the m-ITT analysis set. Appropriate non-linear parametric or non-parametric tests may be applied if the assumptions of the model are not satisfied. Details will be presented in the SAP.

To assess the robustness of treatment effects, a secondary analysis of the primary efficacy endpoint will be performed using the PP analysis set. In addition, two separate *a priori* analyses will be conducted using the model described above with the m-ITT analysis set: one with baseline CT fibrosis scores as a covariate, and one with baseline mRSS as a covariate.

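### The stated 82.3% / 95.6% power is credited to a mean-change F-test that has about 56% / 78% on the table's own inputs, and SAP 10.1 gives conflicting descriptions of the primary contrast

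*Protocol*

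**What the plan says.** **The test.** Protocol 10.4.2 states that "an F-test will be used to test the hypothesis that the mean change from baseline during the treatment period differs between the two treatment groups". In Protocol 10.5.4, repeated in SAP 7, power is defined by the same test: "The average power is calculated as the number of simulations where the F-test used to test the hypothesis that the mean change from baseline" differs between arms is rejected, over all simulations. That section also says "We used a compound symmetry variance-covariance structure" and concludes for Scenario 1 that "a sample size of 75 patients per treatment arm is required to obtain a minimum power of 80"%.

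**Wording that points elsewhere.** The caption of Table 10.5.4 (SAP Table 7.1) reads "Power to detect differences in the response pattern from baseline to 18 months for the primary outcome". Protocol 10.2 says its Δ "reflects the adjusted mean change from baseline trajectory over the 18-month treatment period".

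**Correlations.** The column heading in Table 10.5.4 begins "Assumed Correlations (AR1", above values of 0.866, 0.834, 0.802, 0.790 and 0.780.

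**SAP 10.1.** The model equation gives month a single coefficient and names μ3, the treatment-by-month term, as the parameter of interest. The next paragraph says the F-test is of mean change over the treatment period. The results row asks for mean change but labels it as a slope. Residual covariance is unstructured, and participants are indexed from 1 to 51.

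**Adequacy.** SAP 7 still says that 140 to 150 participants give adequate power.

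**The concern.** Mean change over six visits, the 5-df interaction and a linear-slope difference are different hypotheses. A between-arm shift that is constant from month 3 onward is what a mean-change test detects, yet it gives no treatment-by-month interaction. The study hypothesis is of faster and/or greater improvement, so the contrast decides which kind of benefit the trial can find.

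Two things follow. A reader of the power table would take 75 per arm as enough for a mean-change test when, on the listed inputs, it may not be. And if the SAP's conflicting wordings stand at unblinding, more than one primary p-value could be defended. SAP 8.6 makes no multiplicity adjustment precisely because there is one primary analysis.

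**Working it through.** **Inputs** (Table 10.5.4, months 3 to 18)
- Arm differences: Scenario 1: 0.5, 1.375, 2.25, 2.5, 2.5, 2.5 (mean 11.625/6 = 1.9375). Scenario 2: 0.75, 1.75, 3.0, 3.125, 3.25, 3.25 (mean 15.125/6 = 2.5208).
- SDs: 4.1, 5.1, 6.2, 6.9, 6.2, 6.2. Lag correlations as listed.
- Cumulative dropout: 6.5, 13, 17, 20, 23, 24%. Retention averages 82.75%, which matches the plan's 83%.
- Two-sided 5% test.
- Assumptions: the correlations apply to change scores, and baseline FVC-% explains none of the variance (R² = 0), because the documents give no value.

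**Mean-change test.** With monotone dropout, the information per arm is n Σ p_k S_k⁻¹. Here p_k is the share whose last visit is k, and S_k is the leading k×k block of the covariance, padded with zeros. The variance of the difference is twice the inverse. For the six-visit mean at 75 per arm, SE = 0.916.
- Scenario 1: 1.9375/0.916 = 2.11; noncentral F (1 numerator df) gives 55.6%.
- Scenario 2: 2.5208/0.916 = 2.75; power 78.0%.
- Normal check: Φ(2.11 − 1.96) ≈ 56%; Φ(2.75 − 1.96) ≈ 79%.
- Without dropout it would still be only 59.4% / 81.6%.
- For 80% power at R² = 0 this test needs about 133 (Scenario 1) or 79 (Scenario 2) per arm.

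**Linear slope, unstructured matrix.** The GLS slope differences are 0.1334 and 0.1682 points per month with SE 0.0469. The ratios 2.85 and 3.59 give 80.7% and 94.6%.

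**Which test fits the published cells?** The 5-df column is a simulation on the same inputs, fitted by REML with compound symmetry, 5,000 trials per cell. The other two computed columns are analytic GLS.

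| Scenario, n per arm | Published (95% bounds) | Mean change | 5-df interaction, compound symmetry | Linear slope, unstructured |
|---|---|---|---|---|
| 1, 75 | 82.3 (79.8-84.6) | 55.6 | 82.1 | 80.7 |
| 1, 70 | 78.6 (75.9-81.1) | 52.7 | 79.6 | 77.9 |
| 1, 65 | 76.3 (73.5-78.9) | 49.7 | 75.9 | 74.8 |
| 2, 75 | 95.6 (94.1-96.8) | 78.0 | 95.4 | 94.6 |
| 2, 70 | 92.6 (90.8-94.2) | 75.1 | 93.3 | 93.1 |
| 2, 65 | 91.8 (89.9-93.4) | 71.9 | 92.5 | 91.2 |

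The last two columns fall inside all six intervals; mean change falls inside none. Fitted with compound symmetry, mean change still gives only 57.6% / 80.0% at 75 per arm. The other pairings fail: at 75 per arm, the 5-df test under the unstructured matrix gives 71.8% / 91.3%, and the slope under compound symmetry gives 88.5% / 97.0%.

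**Sensitivity to baseline.** Mean-change power at R² of 10, 20 and 30% is 60.0, 65.1 and 70.9% (Scenario 1) and 82.1, 86.3 and 90.4% (Scenario 2). Reaching the stated figures needs about 47% / 44%.

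**AR(1) heading.** AR(1) at 0.866 would give 0.866² = 0.750 at six months; the table lists 0.834.

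**Precision at 51.** Assume a 26/25 split and R² = 0. With the planned dropout, SE = 1.57 and the 95% half-width is 2.01 × 1.57 ≈ 3.2 points. SAP 10.1 indexes the 51 under m-ITT, whose members already have a post-baseline assessment, so the month-3 loss may be counted twice. Rescaling retention to those with a month-3 visit gives SE = 1.52 and a half-width of about 3.1.

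**The case against.** **The published power is not miscalculated.** This stands. Six of six cells are recovered by a treatment-by-month test, and the caption and Protocol 10.2 fit that reading. A reader might infer that the sponsor's arithmetic is wrong, or that the trial was designed with 56% power. The documents do not support either; the fault is in which test the power sentence names.

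**SAP 10.1 does choose.** Largely right. The equation gives month one scalar coefficient, dummy variables are declared for prior MMF but not for month, μ3 is named, and the results row says slope. Read literally, this is linear month with a slope difference, and on that reading the published power holds within 1-2 points. So it would go too far to say the SAP leaves the contrast wholly open. But the sentence defining the F-test still says mean change, as does Protocol 10.4.2.

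**The 56% / 78% depends on unstated inputs.** Also fair. Protocol 10.5.2 describes the correlations as those of repeated FVC-% measurements, which may mean levels rather than changes. If correlations of change were 0.5 (assumed), mean-change power would be about 71% / 90%; at 0.35, about 80% / 95%. Those values are far below what the table lists, and the documents do not give them.

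**Enrolment has stopped, so new power tables change no decision.** This limits the rerun but not the need to fix the contrast. SAP 14 acknowledges the shortfall, and SAP 10.1 already reports a confidence interval. SAP 7 nevertheless keeps its adequacy statements for 140-150 without qualification.

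**Conclusion.** The concern holds as a wrongly attributed power figure and an internal conflict in SAP 10.1. At 75 per arm, all naive, the mean-change test named in the text has about 56% / 78% power against the stated 82.3% / 95.6%, a shortfall of about 27 / 18 points. It narrows to about 11-22 / 5-14 points if baseline explains 10-30% of variance. This rests on the listed lags being correlations of change and on R² values that the documents do not supply.

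Two tests fit the published cells equally well, so which one was simulated remains an inference. Compound symmetry is the structure stated for the simulation, which favours the 5-df interaction; SAP 10.1 favours the slope.

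The all-naive figures should not be carried into the mixed-population Table 10.5.5 / 7.2. There, Protocol 10.5.5 says of prior treatment that "This results in less and less separation between the course of the two treatment arms as the length of time on prior MMF increases", and the curves are in a figure that is not shown.

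**What to change.** Before unblinding:
1. In SAP 10.1 name one primary contrast, state whether month is linear or categorical, and make the F-test sentence, μ3 and the slope label agree.
2. In Protocol 10.5.4 and SAP 7, either correct the power sentence so that it names the test the table belongs to, or restate Table 10.5.4 / 7.1 for the chosen contrast under the unstructured covariance. At 75 per arm and R² = 0 that is about 56% / 78% (mean change), 72% / 91% (5-df interaction) or 81% / 95% (linear slope). State the baseline R² assumed.
3. Correct the AR(1) heading, and say whether the lags are correlations of change or of FVC-% level.
4. Rerun Table 10.5.5 / 7.2, with the sponsor's own curves, only if the chosen contrast is not the one simulated.
5. In SAP 7, mark the 140-150 adequacy statements as design-stage. Give approximate precision for the 51 m-ITT participants: mean-change SE about 1.5-1.6, 95% half-width about 3.1-3.2 points (near-even split, R² = 0).

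The cost is SAP and protocol text edits and, for some choices of contrast, a rerun of existing simulations. No added enrolment is needed.
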